Acute traumatic rib fractures are a common issue for patients of trauma surgeons. They inflict substantial morbidity, the most dreaded and consequential of which are pulmonary complications. While these fractures are often treated non-operatively, there is a continued need for effective adjuvant treatments to improve rib fracture pain and outcomes. Prior studies have evaluated outcome measures for traumatic rib fractures that include respiratory failure, tracheostomy requirement, ICU length of stay, hospital length of stay, narcotic requirement, daily maximum incentive spirometry volume, pneumonia, and mortality [1]. Other studies have evaluated range of motion, kinesiophobia (as evaluated by the Tampa Score), the Respiratory Measurement Movement Index (RMMI), Spirometry, and Pain assessment (Continuous vs. Intermittent) [2].

Rib belts, which have been present since at least 1945, have long been used to provide pain relief via chest wall stabilization [3]. However there is an extreme paucity of literature regarding their clinical efficacy, and their use has largely been abandoned due to concerns that they may have been overly constricting and resulted in poorer respiratory (pulmonary/breathing) outcomes. Newer generation rib belts are more elastic and theoretically less constricting than their earlier generation predecessors, however their clinical efficacy has not been yet demonstrated. We will therefore plan to perform a prospective trial to determine if these rib strapping devices are effective clinical tools in the traumatic rib fracture population. The goal of the study is institutional quality improvement, to determine if we see benefit of these devices for the pain management of our trauma population. We will also conduct this as a pilot trial for hopeful future research applications, however the overall goal is institutional improvement.

Patients determined to be eligible for the study by the patient's clinical provider (and per our previously defined criteria) will be recruited to enroll in the project within the first 24 hours of their hospital admission (i.e. 24 hours following the documented H&P Note). They will be offered the opportunity to consent to enrollment in the study and will be assigned by the study team into either the intervention (RibFx belt +current standard of care) (n=35 subjects) or control (current standard of care) arm (n=15 subjects) in a quasi-experimental prospective design: untreated control group with dependent pretest and posttest samples. In this manner, the intervention arm will be both compared to themselves (pretest vs. posttests) as well as to a control group not exposed to the intervention.

Patients upon enrollment in the study will undergo an initial assessment that will include their baseline pain scores, narcotic

consumption, incentive spirometry scores, and the subjective self-reported results of their questionnaire (the pre-test questionnaire- see attached). Patients will continue to be scored on objective (incentive spirometry results, opioid pain medicine consumption) and subjective variables (pain scores) during their hospital course. Between 24-48 hours after enrollment, they will be prompted to again complete a similar 2nd questionnaire post-test (if they are discharged from the hospital at this point in the time course, they will be sent home with the questionnaire and prompted to complete it at home, or asked for an agreed upon time and day for study staff to call the patient to complete the questionnaire over the phone). At their follow up appointment in trauma clinic (which will be coordinated by the research team to be as close as possible to 3 weeks post injury), they will have the opportunity to again voluntarily complete a final short questionnaires (post-test) that assess their pain control and respiratory function over the last 3 weeks. If the patient does not plan to follow up in trauma clinic (or is not asked to), we will ask the patient for an agreeable time and day to call the patient and administer the questionnaire over the phone. At this point, their involvement in the trial will be complete.

All aspects of data collection will be performed only by approved members of Key Personnel.

Patients themselves will play an active role in data collection during the trial, and will be instructed and prompted in how to do so. One key change from the prior iteration of the protocol was that before, UVM staff nurses would collect research data while the patient was inpatient. Because they are not research personnel, we will no longer ask them to do so. Patients will be expected to fill out a worksheet on a daily basis, both while inpatient and after discharge, on their daily incentive spirometry scores as well as their minimum and maximum pain scale scores. This will be used to supplement the survey or questionnaire data, as well as the objective data from the EMR.

We will ultimately compare groups using a quasi-experimental design as follows: Untreated control group with dependent pretest and posttest samples. This will allow for a direct comparison of patient to patient within the intervention arm (patient pretest result serving as control compared to posttest result) (n=35 patients). To observe for temporal variability, we will have a control group with no intervention as well (no rib belt worn) (n=15), however the principle aim of the study is the comparison of patients to themselves in a pre-test, post-test fashion.

PURPOSE AND OBJECTIVES

Purpose: *The importance of the research and the potential knowledge to be gained should be explained in detail. Give background information.*

The purpose of this study is to ascertain whether the use of next generation rib orthosis belts (such as the RibFx) can improve patient outcomes following traumatic rib fractures within our population, whether it be by improving pain control, decreased respiratory complications, or increased patient satisfaction. We hypothesize that the use of elastic rib belts will improve rib fracture pain control without compromising pulmonary function (statistically significant improvement in pain control without significant impairment in respiratory function or increase in respiratory complication). We feel as though answering this question can help us as providers to improve the quality of care to our patients in our department.

Rib fractures are a common traumatic injury, and can cause substantial morbidity and mortality in the trauma population. As rib fractures most often are not treated with surgical intervention, there is demand for non-operative strategies to promote healing, pain control, and mechanical/musculoskeletal support. This can also help decrease the administration of potentially harmful pain medications such as opioid or narcotic pain medication. Further, as rib fracture pain can often be long lasting, this can truly increase quality of life for patients as they recover from these injuries.

References. *Include references to prior human or animal research and references that are relevant to the design and conduct of the study.*

3. Quick, G (1990). A randomized clinical trial of rib belts for simple fractures. *The American Journal of Emergency Medicine.*

Objectives: Clearly state the primary and secondary objective(s) of the study.

The objectives of the clinical trial are to determine if rib orthosis via the use of the RibFx belt can improve patients after traumatic rib fractures by improving pain control without compromise of respiratory function or increase respiratory complications of rib fracture.

Primary objective: Compare pain control in patients with non-operatively managed traumatic rib fractures via subjective/qualitative self-reporting of pain control via pain scores and questionnaires, as well as narcotic consumption requirements.

Secondary objectives: Compare pulmonary hygiene and function amongst patients with non-operatively managed traumatic rib fractures via incentive spirometry scores and incidence of post-traumatic pneumonia and radiological evidence of atelectasis incidence

METHODS AND PROCEDURES

Study Design: *Describe the research design, including a description of any new methodology and its advantage over existing methodologies.*

Per Jeffords Institute for Quality Data, there were 190 patients admitted to the Acute Care Surgery (Trauma) service at the University of Vermont Medical Center during the year 2016. Assuming that these numbers remain fairly static overtime as they have in the past, we would expect approximately 16 patient admissions per month with the diagnosis of rib fracture (seasonal fluctuations do exist with more traumatic admissions during the summer months). The goal time period for the trial would be to conduct this trial during the summer, with a goal of 50 total patients. We would therefore expect an enrollment period (data collection phase) of approximately 3 months.

During the study (following appropriate IRB approval), appropriate patients will be recruited both to the control arm of the study and the intervention/comparison arm in a specified / non-randomized sequence as seen in the schematic below (First 5 patients control, next 5 patients intervention, next 5 patients control, next 5 patients intervention, next 5 patients control, final 25 patients intervention). Control arm will include 15 total patients. All will be consented to the study upon admission (first 24 hours of index hospitalization for injury) with full knowledge that they will either be undergoing no intervention other than receiving the current standard of care for rib fracture care per our institution's standard, and if assigned to the rib belt group, expected to wear the rib belt during their recovery.

The current standard of care for rib fractures at our institution is as follows: includes oral and IV analgesia and other multimodal pain control as appropriate, including muscle relaxants such as methocarbamol (robaxin) unless there is a contraindication, pulmonary hygiene/toilet and respiratory care (including frequent evaluations by physicians, respiratory therapists, and nursing staff, early mobilization, and monitoring for pulmonary complication (via vital signs, pulse oximetry, oxygen requirement, chest imaging if appropriate).

[figure not shown]
All patients will undergo initial "Pre-test" testing which will include baseline pain scores (1-10 traditional pain scale), initial narcotic consumption (in MME) for first 24 hours of hospitalization, maximum incentive spirometry score for first 24 hours of hospitalization, and pre-test questionnaire result (see attached questionnaire #1). As the study continues their relevant data will be collected, including both objective (incentive spirometry scores, opioid pain medication consumption, incidence of atelectasis and pneumonia) and subjective (pain scores, survey result) clinical data. Concurrently, we will complete the trial with the intervention (RibFx belt) phase in which participants will be enrolled in the interventional arm of the study. The objective and subjective data will be collected in an identical fashion- the only difference between groups will be that this group will have been fitted with the RibFx belt for their hospital course and discharge.

The participants (both in the control and interventional groups) will again be asked to complete essentially the same brief surveys in a post-test fashion at two set time points: between 24-48 hours after initial enrollment in the study (Questionnaire #2)(if patient has been discharged at this point, they will be sent home with this survey and instructed when to complete, or facilitated completion by calling the patient at this time), and at 3 weeks post-injury (this will be done at their clinic visit, assuming they are not still admitted to the hospital at this time point).

Patients will also be sent home with a work-book to record their incentive spirometry scores and pain scores (all patients will be sent home with an incentive spirometer, and all patients in the interventional group will be sent home with their Ribfx belt).

[figure not shown]

The following schematic will be used for enrollment group assignment in the study (n=50 total participants):

During the chart review portion of the study, patients who have authorized to have their medical records reviewed will have their post-traumatic records reviewed for the following diagnoses or conditions: respiratory failure, tracheostomy requirement, pneumonia, tube thoracostomy (chest tube), epidural use, intubation rates, hospital length of stay, and mortality.

[figure not shown]
The following schematic represents the patient/subject trial course:

The following additional data will also be quantified from the medical record via manual data extraction: ICU length of stay, hospital length of stay, pulse oximetry and respiratory rate scores (taken from already collected vital signs every four hours), body mass index (BMI), bronchodilator (such as albuterol or other inhaled beta agonist) use, age, sex/gender, tobacco history/pack years, days on mechanical ventilator, narcotic requirement (in mean morphine equivalents or morphine equianalgesic dose per day).

In addition, an independent radiology physician will analyze the chest x-rays, CT chests of the patients enrolled in the study and grade them in a blinded fashion) on a scale for the following characteristics: Degree and quantity of rib fracture, presence and degree of atelectasis, presence of COPD/emphysematous change or other parenchymal lung disease, presence and degree of pneumothorax, bilateral vs. unilateral disease, presence of intrapleural fluid, evidence of "flail chest" segment, and presence of pulmonary contusion and other noted pathology (see the attached Radiology Grading Form document). We will measure the degree of radiological severity and compare the control and interventional group to determine what differences in initial disease severity exist (so they can be accounted for).

GANTT CHART WITH PROJECT TIMELINE FOR RibFx CLINICAL TRIAL

Procedures: Describe all procedures (sequentially) to which human participants will be subjected. Identify all procedures that are considered experimental and/or procedures performed exclusively for research purposes. Describe the types, frequency and duration of tests, study visits, interviews, questionnaires, etc. Include required screening procedures performed before enrollment and while on study. Please provide in table, list or outline format for ease of review. (describe and attach all instruments)

Note: A clinical research protocol may involve interventions that are strictly experimental or it may involve some aspect of research (e.g., randomization among standard treatments for collection and analysis of routine clinical data for research)

(purposes). It is important for this section to distinguish between interventions that are experimental and/or carried out for research purposes versus those procedures that are considered standard therapy. In addition, routine procedures performed solely for research purposes (e.g., additional diagnostic/follow-up tests) should be identified.

Each patient in the interventional arm will be fitted with a RibFx orthosis belt, which is to be worn during the majority of their day (excluding showering/bathing). It will be encouraged (though not mandatory) to wear at night. Patients in both the control and interventional arm will be expected to participate in pulmonary hygiene / toilet exercises with guided and independent incentive spirometry as per our normal routine and standard of care. There are no other interventions or procedures that the patients will be subjected to for the research trial- other procedures/interventions will be performed only if the clinical care team feels they are indicated.

For research involving survey, questionnaires, etc.: *Describe the setting and the mode of administering the instrument and the provisions for maintaining privacy and confidentiality. Include the duration, intervals of administration, and overall length of participation. (describe and attach all instruments)*

Not applicable

Patients will be assessed with three short questionnaires in a pretest , posttest fashion at both the onset of the study, 24-48 hours after enrollment, and at their follow-up appointment 3 weeks after (2 post test questionnaires). The initial evaluation will occur on initial assessment prior to placement of the rib belt (or, for the control/ non-intervention group, at the onset/first 24 hours of the study).

Each of the questionnaires is essentially the same with only brief modifications made in the first two questions to make them appropriate for the timing during the clinical course. However these are all attached (see Questionnaire 1,2, and 3). Questionnaires 2 and 3 may be facilitated over the phone if the patient is discharged before the defined time frames are met.

Patients in both the intervention and control arms will present in post-admission follow up at a time period of 3 weeks post injury (range, 2-4 weeks) following their hospital admission, and will be asked to fill out a brief survey regarding their respiratory function and pain control. This survey will also inquire into compliance with the use of incentive spirometer, and compliance with the use of the RibFx belt (for patients in the intervention arm). If patients are not asked to present to trauma clinic for follow up, or if a patient does not intend to follow up, we will aim to complete this questionnaire over the phone in the same time frame.

The surveys are a novel series of questionnaires using previously validated tools such as the COPD Assessment Test or CAT (Jones PW, Harding G, Berry P et al 2009) and the Brief Pain Inventory (BPI) in order to subjectively assess each patient's own breathing/ respiratory and pain symptoms. The surveys also have additional questions gaging their pain medication usage, compliance with their treatment therapies (including IS and rib belt usage, when applicable). The survey is designed to be completed in ten minutes. The survey was constructed with the assistance of a professor psychologist who specializes survey construction (Author [name]). There will be no financial compensation for survey completions.

All surveys will be adapted to apply to the unique population being surveyed- the post-trauma population. This may involve removal of some questions that are not applicable to the rib fracture patients. There are several questions on the questionnaire that might not be applicable to the control group- they are simply instructed to not complete those four questions.

The surveys have been modified in order to be more easily comprehended to the average patient, and to require minimal additional instruction (so that the patient can complete them independently with no additional prompting).

The surveys that will be utilized are attached to the research protocol (see supplemental documents- Questionnaires 1,2, and 3).

Statistical Considerations: *Delineate the precise outcomes to be measured and analyzed. Describe how these results will be measured and statistically analyzed. Delineate methods used to estimate the required number of subjects. Describe power calculations if the study involves comparisons. Perform this analysis on each of the primary and secondary objectives, if possible.*

In this study, we will utilize a quasi-experimental design to compare 35 subjects to themselves in a pre-test, post-test fashion. In addition, we will have an additional 15 non-interventional control patients to observe for temporal changes in patient's symptoms not secondary to the intervention itself. However, it is important to note that the study is not powered to detect differences between the control group and the intervention group. The purpose of the control group is to observe for differences that occur in this population over time regardless of intervention (it should be assumed that pain will improve as time increases from the set injury point, regardless of intervention). Further, this preliminary data could potentially be used to calculate an accurate power calculation for a definitive randomized controlled trial.

Groups will be compared by demographical and clinical data to determine what potentially confounding differences exist between the arms of the study. Relevant objective data that will be used to determine group differences include (but not limited to): age, sex, tobacco use status (active/former/none), presence of asthma, presence of COPD, or presence of restrictive lung

disease, home oxygen use, obstructive sleep apnea/ CPAP use, chronic pain incidence, narcotic/opioid medication consumption, obesity/ BMI. We will also measure relevant variables of their clinical course such as regional block/anesthesia/epidural administration. Radiological appearance of presenting imaging (either CT Chest or chest X-ray) will be compared by a dedicated and blinded radiologist who will grade the initial imaging based on severity including the following variables: number of fractures, bilateral vs. unilateral, degree of displacement, presence of lung contusion, presence of pneumothorax, presence of intrinsic lung disease, pleural effusion or blood.

Survey results (both pretest and posttests) will be compared using the appropriate statistical methods depending on the questions construct: with Chi squared performed for categorical variables (such as multiple choice) and unpaired t test for continuous variables (such as likert scale rankings).

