Subjects targeted for the study are those that would benefit most from the intervention (Rib belt)- patients with traumatic rib fractures. In order to determine if the belt has efficacy in this population, we must utilize the belt in this target population. Patients at the extremes of age (<18 or >80 years old) have been ruled out as they may create unreasonable confounding when measuring the relevant study outcomes, as well as potentially creating issues with autonomy and consent processes. There are also other exclusion criteria as dictated below.

Vulnerable Populations: Explain the rationale for involvement of special classes of subjects, if any. Discuss what procedures or practices will be used in the protocol to minimize their susceptibility to undue influences and unnecessary risk (physical, psychological, etc.).

Not applicable

Number of Subjects: What is the anticipated number of subjects to be enrolled at UVM/UVM Medical Center and in the case of a multi-center study, with UVM/UVM Medical Center as the lead, the total number of subjects for the entire study.

The current anticipated number of subjects is 35 patients in the intervention arm, and 15 in the control arm of the study, for a total of 50 patients. All these subjects will be enrolled at UVMMC.

Inclusion/Exclusion Criteria: Eligibility and ineligibility criteria should be specific. Describe how eligibility will be determined and by whom. Changes to the eligibility criteria at a later phase of the research have the potential to invalidate the research.

Inclusion Criteria:

Adult person age 18-80 admitted with at least one acute traumatic closed rib fracture to the University of Vermont Medical Center

Exclusion Criteria:

Pediatric (<18 year old) and Geriatric (>80 year old) patients

Patients who are intubated on arrival or within first 24 hours of admission or with Glasgow Coma Scale (GCS) < 14 (altered or depressed consciousness)

Pregnant patients

Patients who undergo operative rib fixation for their rib fractures (such as open reduction internal fixation, or rib plating)
 Patients with chest wall deformity, lacerations, burns, or soft tissue injuries that preclude placement of the RibFx belt
 Patients with an additional mechanism of injury that would create severe distracting pain, as determined by the admitting team.
 Isolated 1st rib or 2nd rib fractures

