After verbally explaining the rational, reasoning, risks, and potential benefits of the study, patients will have ample opportunity to decide whether or not to enroll without feeling pressured into enrolling (up to 24 hours will be permitted for deciding). Relevant written materials will be left for further review, including a written consent form, device pamphlet, and information pamphlet (All included in the IRB materials). Upon request of the patient, a member of the research team will always be available to answer further questions regarding the study via a "hot line" and also via the clinical care team.

Information Withheld From Subjects: Will any information about the research purpose and design be withheld from potential or participating subjects? If so, explain and justify the non-disclosure and describe plans for post-study debriefing.

Not applicable

No information will be withheld from subjects. N/A

Attach full grant application, including budget information and/or any contract or draft contract associated with this application.

All materials must be submitted electronically to the IRB via InfoEd. Proper security access is needed to make electronic submissions. Visit the [InfoEd Resource Materials](#) page for more information.

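### The plan says pain falls with time from injury, but it neither lists time since injury nor uses it in the belt-control comparison, which matters mainly for Questionnaire 3.

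*Combined protocol and SAP*

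**What the plan says.** - **Enrolment and pre-test.** The opening overview places enrolment "within the first 24 hours of their hospital admission (i.e. 24 hours following the documented H&P Note". The initial assessment, including the first questionnaire, is done on enrolment.
- **Questionnaire 2.** The same overview counts from enrolment: "Between 24-48 hours after enrollment, they will be prompted to again complete a similar 2nd questionnaire post-test".
- **Questionnaire 3.** The survey part of Procedures sets it "at a time period of 3 weeks post injury (range, 2-4 weeks) following their hospital admission". The overview adds that the visit should be booked as near to 3 weeks after injury as can be managed.
- **Eligibility.** Inclusion Criteria require a patient "admitted with at least one acute traumatic closed rib fracture". Study Design refers to the index hospitalization for the injury. Neither gives a maximum number of hours or days from injury.
- **Role of time.** Statistical Considerations says "it should be assumed that pain will improve as time increases from the set injury point, regardless of intervention".
- **Variables and tests.** Time since injury is not in the chart-extraction list (Study Design) or in the list of possible confounders (Statistical Considerations), although the second list is open-ended. The tests named for the survey results are chi-squared and an unpaired t test, neither of which has a time term.

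**The concern.** The plan names time from injury as a driver of its main outcome, but does not list it as a variable or use it in comparing the arms. Enrolment follows the admission note and Questionnaire 3 follows injury. The change from pre-test to Questionnaire 3 therefore covers a different stretch of recovery in different patients, for reasons unrelated to the belt.

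Within an arm this adds noise. Between arms it adds bias if late presenters, or early and late clinic visits, are unevenly spread over 15 controls and 35 belt patients. Allocation makes that possible: the first 25 patients alternate in fives, and the last 25 all receive the belt. A later shift in referral or clinic scheduling would fall on one arm only. Without time since injury in the data set, nobody could see it or adjust for it.

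**Working it through.** **1. Windows implied by the text.** Let D be the days from injury to the admission note; the plan sets no limit on D.

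- Pre-test: D to D + 1 days after injury.
- Questionnaire 2: 1 to 2 days after enrolment, so D + 1 to D + 3 days after injury.
- Questionnaire 3: 14 to 28 days after injury.
- Pre-test to Questionnaire 3: shortest 14 − (D + 1) = 13 − D days, longest 28 − D days.

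| D | Pre-test to Q2 | Pre-test to Q3 |
|---|---|---|
| 0 | 1–2 days | 13–28 days |
| 7 (illustration) | 1–2 days | 6–21 days |

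The interval to Questionnaire 2 does not depend on D. Only its place on the recovery curve does.

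**2. Size for two single patients.** The documents give no recovery curve. Assume pain(t) = 2 + 5·exp(−t/τ), with t in days from injury and τ from 7 to 14 days. Compare a first test at day 0.5 with one at day 4.5.

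| Natural fall | τ = 7 | τ = 14 |
|---|---|---|
| Day 0.5 to 21 | 4.41 | 3.71 |
| Day 4.5 to 21 | 2.38 | 2.51 |
| Difference, Q3 | 2.0 | 1.2 |
| Day 0.5 to 2.0 | 0.90 | 0.49 |
| Day 4.5 to 6.0 | 0.51 | 0.37 |
| Difference, Q2 | 0.4 | 0.1 |

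The two ends of the Questionnaire 3 window, day 14 and day 28, differ by 0.59 (τ = 7) to 1.16 (τ = 14) points.

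**3. Size for arm means.** Bias is the difference between arms in the proportion of late presenters, times the per-patient gap. Suppose 2 of 15 controls and 2 of 35 belt patients are late (assumption): 2/15 − 2/35 = 0.133 − 0.057 = 0.076. Then 0.076 × 1.2 = 0.09 and 0.076 × 2.0 = 0.15 points, here in favour of the belt because late controls have less recovery left to show.

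**4. Noise from the Questionnaire 3 window.** The plan's own power figure comes first. A 20% fall in a mean MPQ PRI of 28 is 5.6. The SD of change is 16 × √(2 × (1 − 0.8)) = 10.12. A two-sided paired t test at 0.05 gives 83.4% power at n = 30 and 88.9% at n = 35, against 83% and 88% stated, so the plan's figures reproduce. If visits spread evenly over the 14-day window, their SD is 14/√12 = 4.04 days. With an assumed slope of b PRI points per day, the SD of change becomes √(10.12² + (4.04b)²).

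| b | SD of change | Power, n = 35 |
|---|---|---|
| 0.5 | 10.32 | 88% |
| 1.0 | 10.90 | 84% |
| 1.5 | 11.80 | 78% |

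**The case against.** The strongest reply is that the plan already limits the problem. The fracture must be acute, enrolment belongs to the index hospitalization, the final visit aims at 3 weeks with 2 to 4 weeks only as tolerance, the confounder list is open-ended, and the belt-control comparison is declared unpowered. Nothing in the documents shows that patients presenting days late are common. All of this stands and is why the effect is judged modest. It does not put time since injury into the data set or the comparison.

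Four stronger readings are tempting and are not supported.

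- **That the pre-test and Questionnaire 2 run on different clocks.** They share the enrolment clock, because the first questionnaire is completed on enrolment. The exceptions are baseline opioid use ("initial narcotic consumption (in MME) for first 24 hours of hospitalization") and baseline maximum spirometry, both tied to the first day in hospital.
- **That the bias is as large as the target effect.** The 1.2 to 2.0 points separate two hypothetical patients. An arm-mean bias of 1.2 points (20% of a score of 6) would need late-presenter proportions to differ by about 60 percentage points even at the larger gap (1.2/2.0 = 0.6). The plan's 20% effect is also set on MPQ PRI, not on the 1–10 pain scale.
- **That consent timing is impossible.** Consent Procedures says "up to 24 hours will be permitted for deciding", which is a maximum. It fits if the decision period ends when the 24-hour enrolment limit does. This is wording.
- **That an eligibility cap on late presenters is needed.** In a single-centre pilot, recording and reporting the interval is enough.

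**Conclusion.** The concern holds in a limited form. The plan identifies time from injury as a driver of pain, but omits it from both variable lists and from the belt-control comparison. The pre-test to Questionnaire 3 interval can be 13–28 days for one patient and 6–21 days for another whose admission note comes 7 days after injury.

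The effect on arm means is probably modest, around 0.1 points in the illustrated imbalance. It depends on the number and spread of late presenters, which the documents do not give. The effect is smaller still for Questionnaire 2, where even two single patients differ by only 0.1 to 0.4 points. The Questionnaire 3 window alone costs little power unless recovery at that stage is steep. The pain curve, the 4-day delay, the imbalance and the PRI slopes are all assumptions.

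A reader might infer that adjusting for time would make the within-belt pre-post contrast interpretable. It would not: natural recovery enters that contrast even if every patient is tested on an identical schedule. That is a separate matter.

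**What to change.** 1. Record the date and time of injury and of every assessment. Injury date is already needed to book the 3-week visit.
2. Add time from injury to pre-test to the confounder list in Statistical Considerations, and report it by arm. Report the actual day of Questionnaire 3 by arm as well.
3. Replace the unadjusted unpaired t test for belt versus control with a regression of the change on arm, baseline score, time from injury to pre-test and, for Questionnaire 3, actual days since injury. The visit day is settled after the belt is fitted, so also show the result without that last term.
4. As tidying, end the decision period in Consent Procedures at the 24-hour enrolment limit, and say whether the 2 to 4 week range counts from injury or admission.

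The cost is one baseline field, time stamps on forms already in use, and one or two timing covariates in a 50-patient comparison that the plan says is not powered. No patients are lost. The adjustment improves the belt-control estimate and its use in planning a definitive trial; it does not repair the pre-post contrast.
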